GDPR	EU General Data Protection Regulation 2016/679
HBM	Human Body Material
IC(F)	Informed Consent Form
ICH	International Council on Harmonisation
ISF	Investigator Site File
IUD	Intra-uterine device
IMP	Investigational Medicinal Product
IMD	Investigational Medical Device
IVRS/IWRS	Interactive Voice/Web Reporting System
LAG	Laboratoriumgeneeskunde
LPLV	Last Participant Last Visit
MRI	Magnetic Resonance Imaging
PI	Principal Investigator (of participating research site)
PRO	Participant Reported Outcome
SAE	Serious Adverse Event
SAP	Statistical Analysis Plan
SAR	Serious Adverse Reaction
SOP	Standard Operating Procedure
TMF	Study Master File
VIB	Vlaams Instituut voor Biotechnologie

WUG	Wet uitoefening gezondheidszorgberoepen
PCWP	Pulmonary Capillary Wedge Pressure
LVFP	Left ventricular filling pressures
CO	Cardiac output
SV	Stroke volume
VO2	Oxygen uptake
HFpEF	Heart failure with preserved ejection fraction
EDPVR	End-diastolic pressure-volume relationship
CI	Chronotropic incompetence
iLVESV	Indexed left ventricular end-systolic volume
PVC	Premature ventricular contractions
iCPET	Invasive cardiopulmonary exercise test
LAVI	Left atrial volume index
LVMI	Left ventricular mass index
RWT	Relative wall thickness
GLS	Global longitudinal strain
LV	Left ventricle
TR	Tricuspid regurgitation
SaO2	Arterial oxygen saturation
SvO2	Mixed venous oxygen saturation
RPM	Rotation per minute
APMHR	Age predicted maximal heart rate
NYHA classification	New York Heart Association classification
RER	Respiratory Exchange Ratio
AV-delay	Atrioventricular delay
SWV	Shear wave velocity

FUNDING & SUPPORT

Funder or service provider

[name]. [name]

Type of Support (financial or non-financial)

Financial

Reasonable travel expenses (such as public transport, parking fees or mileage reimbursements) incurred by study participants and directly related to participation in the study, will be reimbursed by the Sponsor. Moreover, compensation for time investment will be provided (€13 per hour) and participants will receive an additional compensation for discomfort caused by the invasive measurements (€100).

A travel reimbursement payment log will be kept by the Investigator Site staff (as applicable) and made available for monitoring and verification purposes.

ROLES & RESPONSIBILITIES

The Principal Investigator (PI) is responsible for the conduct of the study at his/her participating research site, and for protecting the rights, safety and well-being of the study participants. As such the PI must ensure adequate supervision of the study conduct at the participating site. If any tasks are delegated, the PI will maintain a log of appropriately qualified persons to whom he/she has delegated specified study-related duties. The PI will ensure that adequate training is provided and documented for all study staff, prior to conducting assigned study-related activities.

It is the Sponsor-Investigator's responsibility to supervise the general conduct of the study (e.g. study progress, communication, protocol training and support of the participating research sites, annual reporting to the Ethics Committee (EC), end of study notification(s) and results reporting, etc.). The UZ/KU Leuven Sponsor-Investigator fulfills mostly both Investigator and Sponsor responsibilities, as outlined in latest version of the International Council on Harmonisation – Good Clinical Practice (ICH-GCP) E6 and applicable regulations.

PI and Sponsor-Investigator shall each be referred to as «Investigator(s)».

STUDY SYNOPSIS

Title of clinical study («study»)	The impact of accelerated pacing and AV-delay regulation on the pulmonary capillary wedge pressure during exercise in patients with HFpEF
Protocol number / acronym	APAVE
Sponsor name	UZ Leuven (University Hospital Leuven)
Sponsor-Investigator	[name]. [name]
Contact address:	[name]
Contact email:	[contact]
Contact [contact]
Study nbr in public database	<Insert unique reference number assigned by public database in which the study is registered>
Medical condition or disease under investigation	Heart failure with preserved ejection fraction (HFpEF)
Study rationale	HFpEF, characterized by elevated left filling pressures and exercise intolerance, is an increasingly common clinical syndrome. Exercise intolerance is the primary symptom and significantly impacts quality of life. An elevated pulmonary capillary wedge pressure (PCWP), a marker of increased left atrial pressure (LAP), is associated with reduced exercise capacity, likely due to pressure transmission to the lungs, and increased mortality. Research has shown that increasing the heart rate at rest can reduce LAP in patients with HFpEF, potentially enhanced by a shortened AV delay. However, patients mainly experience symptoms during low-intensity exercise, where the effects of accelerated pacing remain unknown.
Primary objective	To assess the impact of accelerated pacing with AV-regulation on the PCWP during exercise in patients with HFpEF, particularly at lower intensities of exertion, to offer insights into pacing-based interventions to ultimately enhance exercise tolerance and quality of life.
Secondary objective(s)	To assess the impact of accelerated pacing with AV-regulation on cardiac output, stroke volume, peripheral oxygen extraction and shear wave velocity.
Endpoints	The primary endpoint is the change in pulmonary capillary wedge pressure for each pacing frequency compared to the intrinsic heart rate, assessed at rest and during exercise (cycle ergometry at 10 and 25 Watts of resistance). Secondary endpoints include changes in cardiac output, stroke volume, and peripheral oxygen extraction from the intrinsic heart rate to the pacing frequency associated with the greatest reduction in PCWP, both at rest and during exercise (cycle ergometry at 10 and 25 Watts). Additionally, changes in shear wave velocity at each pacing frequency relative to the intrinsic heart rate will be assessed.
Sample Size	20

Date of anticipated First Participant First Visit (FFPV)	01/10/2025
Date of anticipated Last Participant Last Visit (LPLV)	30/09/2026
Expected study duration for a single participant	3 weeks

STUDY FLOWCHART

Schedule of events – Study specific procedures & assessments

UZ Leuven

Procedures/ Assessment	Screening	Study visit
Visits / Contacts	Visit 1	Visit 2
Timing (weeks)		Week 3
Visit Window (days)	1 day	1 day
Informed consent	X ¹	
Inclusion / Exclusion criteria	X	
Demographics	X	
Medical / Surgical history	X	
Physical examination	X	
Weight / Height	X	X
Vital Signs	X	X
12-lead ECG	X	X
Haematology sampling	X	
Coagulation sampling	X	
Chemistry sampling	X	
(Serious) Adverse event (S)(AE) assessment		X
Invasive CPET (2)		X
Transthoracic echocardiography	X	X
Arterial blood sampling		X
Venous blood sampling		X

Footnotes

Study-specific procedures are labelled in blue; non-study-specific procedures are labelled in green. An ECG, transthoracic echocardiography (TTE), and haematology, coagulation, and chemistry sampling are expected to be performed as part of standard of care. If these assessments have not been performed, or if no recent results are available (within ≤ 3 months), they will be conducted and considered study-specific procedures.

(1) Informed consent must be obtained prior to performing any other study-related procedures

(2) Invasive CPET on a semi supine cycle ergometer

Jessa Hospital

Procedures/ Assessment	Screening	Screening visit 2 (only when necessary)	Study visit
Visits / Contacts	Visit 1	Visit 2	Visit 3
Timing (weeks)		Week 1	Week 3
Visit Window (days)	1 day	1 day	1 day
Informed consent		X ¹	X ¹ (when no visit 2 necessary)
Inclusion / Exclusion criteria	X		
Demographics	X		
Medical / Surgical history	X		
Physical examination	X		
Weight / Height	X		X
Vital Signs	X		X
12-lead ECG	X	(X)	X
Haematology sampling	X	(X)	
Coagulation sampling	X	(X)	
Chemistry sampling	X	(X)	
(Serious) Adverse event (S)(AE) assessment			X
Invasive CPET (2)			X
Transthoracic echocardiography	X	(X)	X
Arterial blood sampling			X
Venous blood sampling			X

Footnotes

Study-specific procedures are labelled in blue; non-study-specific procedures are labelled in green. An ECG, transthoracic echocardiography (TTE), and haematology, coagulation, and chemistry sampling are expected to be performed as part of standard of care. If these assessments have not been performed, or if no recent results are available (within ≤ 3 months), they will be conducted and considered study-specific procedures in screening visit 2. The informed consent form (ICF) will be signed either at the start of visit 2 or at the start of the study visit, depending on whether a second screening visit is required.

(1) Informed consent must be obtained prior to performing any other study-related procedures

(2) Invasive CPET on a semi supine cycle ergometer

I Background, rationale & risk assessment

The role of filling pressures and heart rate in exercise intolerance among patients with HFrEF

Heart failure with preserved ejection fraction (HFrEF), defined by a left ventricular ejection fraction $\geq 50\%$ along with evidence of elevated left ventricular filling pressure (LVFP) either at rest or during stress, is a prevalent and increasingly recognized clinical syndrome, affecting 1–3% of the global population. HFrEF accounts for approximately 50% of all heart failure cases, with its prevalence rising due to aging populations and increasing comorbidities such as hypertension, obesity, and type 2 diabetes. The disease burden is significant, leading to frequent hospitalizations, high healthcare costs, and substantial morbidity and mortality (1).

Exercise intolerance is a hallmark symptom of HFrEF and a major contributor to a reduced quality of life (2, 3). Elevated pulmonary capillary wedge pressure (PCWP), a surrogate for left atrial pressure, has been independently associated with impaired exercise capacity, regardless of traditional determinants of oxygen uptake (4). This association is likely driven by backward transmission of pressure leading to pulmonary congestion, impaired gas exchange, and ventilation–perfusion mismatch (5). Moreover, exertional increases in cardiac filling pressures have been linked to poorer survival outcomes (6).

Given that most daily activities involve low-to-moderate exertion, focusing on low-intensity exercise is particularly relevant, as functional improvements at these levels are likely to yield the greatest benefits in terms of patient autonomy and quality of life.

Approaches to modulate heart rate in patients with HFpEF

Discontinuation of negative chronotropic medication

One strategy to improve the chronotropic response in HFpEF is the withdrawal of negative chronotropic agents. Interestingly, it has been demonstrated that ivabradine further reduces exercise tolerance in HFpEF (17). Although a previous single-centre, retrospective study assessing peak heart rate and peak VO_2 in patients with HFpEF with and without β -blockers found no significant differences (18), the PRESERVE-HR study, a multicentred, randomized, investigator-blinded, crossover clinical trial, showed a significant increase in peak VO_2 following β -blocker discontinuation in patients with HFpEF and CI (19). Moreover, a lower indexed left ventricular end-systolic volume (iLVESV) may help identify those who experience greater short-term improvements in maximal functional capacity after β -blocker withdrawal (20). Currently, a meta-analysis on the effects of β -blocker withdrawal in patients with HFpEF is underway (21).

Rate-adapted and accelerated pacing

Pacing represents another strategy to modulate heart rate in patients with HFpEF. This approach is particularly feasible, as approximately 23% of these patients already have a pacemaker in place (22). Additionally, atrial fibrillation, present in 40% to 60% of patients with HFpEF, is frequently managed with rate-controlling medications, potentially amplifying the therapeutic impact of pacing interventions in this subgroup (22).

The myPACE trial demonstrated that personalized accelerated pacing at rest, with a median lower rate of 75 bpm compared to the standard setting of 60 bpm, led to improvements in quality of life, NT-proBNP levels, physical activity, and device-detected atrial fibrillation (23). In contrast, the RAPID-HF study investigating pacemaker implantation with rate-responsive pacing in HFpEF patients with CI found no significant improvement in $\text{VO}_{2\text{peak}}$ and VO_2 at VAT (24). This lack of effect may be attributed to several factors, including the small sample size ($n = 29$), the absence of accelerated pacing at rest, and a suboptimal chronotropic response during exercise. Specifically, excessive heart rate increases may compromise CO in HFpEF due to their impaired diastolic filling and a blunted pressure-volume relationship (25-27). Conversely, an insufficient heart rate rise may fail to adequately enhance chronotropic function or reduce PCWP, thereby limiting hemodynamic benefit. To address these uncertainties, we aim to investigate hemodynamic responses across multiple pacing frequencies. Moreover, this study has focused on high-intensity exercise, evaluating outcomes beyond the anaerobic threshold. In contrast, our study targets low-intensity exertion.

Shear wave velocity as a marker of ventricular stiffness in HFpEF

An additional parameter we will evaluate in this study is shear wave velocity (SWV). This imaging technique provides insights into myocardial stiffness by assessing the propagation speed of naturally occurring myocardial shear waves following mitral valve closure. A study by Salerno et al. demonstrated that higher pacing frequencies are associated with increased SWV, indicative of

elevated ventricular stiffness (28). However, these findings were observed in a population without HFpEF. In patients with HFpEF, who are characterized by increased ventricular stiffness and a steep EDPVR, the effects of pacing on ventricular stiffness and SVV is unknown. These insights may aid in the pathophysiological understanding of pacing strategies designed to improve diastolic function and exercise tolerance in patients with HFpEF.

Study rationale and objective

This study aims to assess the impact of accelerated pacing with tailored AV-regulation on the PCWP during exercise in patients with HFpEF, particularly at lower intensities of exertion, which are most relevant for daily activities. By determining whether accelerated pacing improves PCWP during exertion, we aim to provide insights into novel pacing-based interventions that could enhance exercise tolerance and ultimately improve quality of life in patients with HFpEF.

Risk assessment

When performed in experienced centers, right heart catheterization (RHC) is generally considered a safe procedure with low morbidity and mortality rates. A comprehensive analysis of 7,218 procedures, including both retrospective (5,727 cases) and prospective (1,491 cases) data, found an overall serious adverse event rate of 1.1% (95% CI: 0.8%–1.3%). The most frequent complications were related to venous access, such as hematoma and pneumothorax, followed by arrhythmias and hypotensive episodes due to vagal reactions or pulmonary vasoreactivity testing. The vast majority of these complications were mild to moderate in intensity and resolved spontaneously or with appropriate intervention (29). More severe complications are rare. Complete heart block or air embolism can lead to chest pain, shortness of breath, and hypotension. Pulmonary artery perforation, seen in approximately 0.03% of cases, may cause sudden respiratory distress and cardiogenic shock. In these cases, complications may require advanced medical intervention (30).

Radial artery canalization is generally well tolerated; complications are uncommon and include, but are not exclusive to, temporary or permanent vessel occlusion, pseudoaneurysm formation, infection, and, rarely, air embolism. Local pain at the site of cannulation, however, is common and may persist for days (31).

Potential complications of CPET include fatigue, leg pain and shortness of breath. Less common complications include cardiac arrhythmias, anginal chest pain, and bronchospasm. Additionally, CPET may lead to hypotension, occasional premature ventricular contractions (PVCs), and, in rare cases, significant ST-segment depression, which typically resolve after test termination. Overall, CPET remains a safe procedure with a low incidence of complications when conducted under medical supervision (32, 33).

2 Study objectives & design

2.1 Study objectives

In this study, we plan to address the impact of accelerated pacing with AV-regulation on the PCWP at rest and during exercise in patients with HFpEF. We hypothesize that accelerated pacing with AV-delay regulation reduces PCWP at rest and during exercise up to an optimal pacing rate beyond which no further benefit is observed.

In this study, we aim to:

- Evaluate the effect of accelerated pacing with AV-optimization on PCWP at rest.
- Investigate the impact of accelerated pacing with dynamic AV delay programming, while avoiding truncation, on PCWP during exercise at two distinct (low) intensities (10 and 25 Watts) using a semi-supine cycle ergometer.
- Assess the change in CO, SV and peripheral oxygen extraction at the pacing frequency corresponding to the lowest PCWP compared to the intrinsic heart rate. This approach allows examination not only of the effects of pacing on backward cardiac function (as reflected by PCWP), but also on forward cardiac function. By doing so, it excludes the possibility that a reduction in PCWP is merely due to a decreased CO.
- Evaluate the effects of different pacing frequencies on SWV as a non-invasive marker of myocardial stiffness

Ultimately, we aim to offer insights into novel pacing-based interventions to enhance exercise tolerance and quality of life in patients with HFpEF.

2.2 Primary endpoints

The primary endpoints are:

- The change in PCWP at each pacing frequency (+20 bpm, +40 bpm, +60 bpm) with its corresponding optimal AV delay at rest, compared to PCWP at the intrinsic heart rate.
- The change in PCWP at each pacing frequency (+10 bpm, +30 bpm, +50 bpm) using dynamic AV delay programming, while avoiding truncation, compared to PCWP at the intrinsic heart rate during exercise (cycle ergometry at 10 and 25 Watts)

The PCWP at the intrinsic heart rate is defined as the average of the PCWP at the intrinsic heart rate heart rate before and after each pacing step.

2.3 Secondary endpoints

The secondary endpoints are:

- The change in CO at the pacing frequency corresponding to the greatest reduction in PCWP compared to the intrinsic heart rate
- The change in SV at the pacing frequency corresponding to the greatest reduction in PCWP compared to the intrinsic heart rate
- The change in peripheral oxygen extraction at the pacing frequency corresponding to the greatest reduction in PCWP compared to the intrinsic heart rate
- The change in SWV for each pacing frequency. The SWV at the intrinsic heart rate is defined as the average of the SWV at the intrinsic heart rate heart rate before and after each pacing step.

Cardiac output is measured via the direct Fick principle, dividing VO_2 by the peripheral oxygen extraction (SaO_2 - SvO_2). SV is calculated as CO divided by HR.

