6.1 Sample size determination

The sample size calculation is based on the expected difference in PCWP between pacing conditions. A power analysis determined that 16 participants are required to achieve a power of 80% and a significance level of 5% (two-sided), assuming a mean difference of -2 mmHg and a standard deviation of 2.5 mmHg. To account for potential dropout, the study will enroll 20 participants.

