6.2 Statistical analysis

This is a prospective, single-arm, multicentre, interventional study in which each patient serves as their own control:

- A two-sided significance level of 0.05 will be used for all statistical tests.
- Data will be analyzed using Python, SPSS and Stata statistical software.
- Descriptive statistics of baseline variables will be used to summarize baseline characteristics.
 - Categorical variables will be presented as number and percentage.
 - Continuous variables will be presented as mean \pm standard deviation or median with interquartile range, depending on the Shapiro-Wilk test for normality.
- Comparison of hemodynamic parameters (PCWP, CO, SV, peripheral oxygen extraction) and SVV will be performed using paired student t-test or Wilcoxon-Mann Whitney test whichever will be appropriate.
- Pearson's or Spearman's correlation coefficients, whichever will be appropriate, will be computed to assess the relationship between changes in PCWP and changes in SVV

Endpoint	Statistical analysis methods
Primary	paired student t-test or Wilcoxon-Mann Whitney test
Secondary	paired student t-test or Wilcoxon-Mann Whitney test
Exploratory	descriptive statistics, Pearson's or Spearman's correlation coefficient

7 Data handling

A study-specific Data Management Plan (DMP) will be developed by the Sponsor providing a.o. further details on data flows, data handling, processing and discrepancy management.

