 - Set the pacemaker to DDD mode with a lower rate of **20** bpm above the intrinsic heart rate, rounded to the nearest decimal
 - Adjust AV-delay to the optimal setting and measure shear wave velocity
 - 10 seconds after AV delay optimization: PCWP measurement
- Pacing-off:
 - Reprogram the pacemaker to back-up mode
 - Measurement of SWV
 - 10 seconds after pacemaker reprogramming: PCWP measurement
- Pacing-on
 - Set the pacemaker to DDD mode with a lower rate of **40** bpm above the intrinsic heart rate, rounded to the nearest decimal
 - Adjust AV-delay to the optimal setting and measure shear wave velocity
 - 10 seconds after AV delay optimization: PCWP measurement
- Pacing-off:
 - Reprogram the pacemaker to back-up mode
 - 10 seconds after pacemaker reprogramming: PCWP measurement
- Pacing-on:
 - Set the pacemaker to DDD mode with a lower rate of **60** bpm above the intrinsic heart rate, rounded to the nearest whole number
 - Adjust AV-delay to the optimal setting and measure shear wave velocity
 - 10 seconds after AV delay optimization: PCWP measurement
- Pacing-off:
 - Reprogram the pacemaker to back-up mode
 - Measurement of SWV
 - 10 seconds after pacemaker reprogramming: PCWP measurement
 - After 4 respiratory cycles: collection of arterial and mixed venous blood samples
- Pacing-on
 - Set the pacemaker to DDD mode with a lower rate corresponding to previously determined rate with the greatest reduction in PCWP
 - 10 seconds after pacemaker reprogramming: PCWP measurement
 - After 4 respiratory cycles: collection of arterial and mixed venous blood samples
- Pacing-off: reprogram to pacemaker back-up mode

HR, VO₂, RER and will continuously be measured.

Each pacing-off (DDD 40 back-up pacing mode) and pacing-on (temporary DDD pacing via programmer) period will take 40 seconds.

The optimal AV-delay will be determined via iterative evaluation of the mitral valve inflow by transthoracic echocardiography. This will be followed by SWV measurements, performed over a 12-second period.

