PCWP will be measured as the average end-expiratory value over four consecutive respiratory cycles, following a 10-second period to allow for hemodynamic stabilization. By comparing each PCWP value to the average of the PCWP measured during the pacing-off periods immediately before and after the pacing-on phase, we aim to minimize the impact of spontaneous hemodynamic variability and carry-over effects (41). The heart rate associated with the greatest reduction in PCWP will be repeated as the final pacing-on step, during which CO will be measured by collecting arterial and mixed venous blood samples (direct Fick principle). If two pacing rates result in an equal reduction in PCWP, the lower pacing rate will be selected. If no reduction in PCWP is observed with accelerated pacing, the heart rate corresponding to the smallest increase in PCWP will be selected for the final pacing-on period instead. In this final step, PCWP will be measured again to verify that it remains consistent with the initial PCWP at the same pacing rate. Only the initial PCWP measurement at the optimal pacing rate will be used in our analyses assessing changes in PCWP compared to the intrinsic heart rate.

The pacing rate will never exceed the APMHR, calculated based on Takana's equation (42). If this threshold would be reached, the protocol will be stopped at the pacing step prior to exceeding the APMHR, only followed by the final pacing step in which the pacing rate associated with the greatest reduction in PCWP is repeated.

16 APPENDIX 4: Detailed description of the study protocol during exercise

The following section provides a stepwise description of the pacing protocol performed during exercise (Figure 4):

- Pacing-off:
 - Measurement of SWV
 - PCWP measurement after 10s of cycling
- Pacing-on:
 - Set the pacemaker to DDD mode with a lower rate of **10** bpm above the intrinsic heart rate, rounded to the closest decimal and with dynamic AV-delay settings
 - Evaluate mitral inflow pattern on echocardiography for evidence of E-wave truncation; if truncation is observed, the AV-delay will be adapted accordingly.
 - Non-invasive measurement of BP
 - Measurement of SWV
 - 10s after the last change in pacemaker settings: PCWP measurement
- Pacing-off:
 - Reprogram the pacemaker to back-up mode
 - Measurement of SWV
 - 10 seconds after pacemaker reprogramming: PCWP measurement
- Pacing-on:

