 - Set the pacemaker to DDD mode with a lower rate of **30** bpm above the intrinsic heart rate, rounded to closest decimal and with dynamic AV-delay settings

- Evaluate mitral inflow pattern on echocardiography for evidence of E-wave truncation; if truncation is observed, the AV-delay will be adapted accordingly.
- Non-invasive measurement of BP
- Measurement of SWV
- 10s after the last change in pacemaker settings: PCWP measurement
- Pacing-off:
 - Reprogram the pacemaker to back-up mode
 - Measurement of SWV
 - 10 seconds after pacemaker reprogramming: PCWP measurement
- Pacing-on:
 - Set the pacemaker to DDD mode with a lower rate of **50** bpm above the intrinsic heart rate, rounded to the closest decimal and with dynamic AV-delay settings
 - Evaluate mitral inflow pattern on echocardiography for evidence of E-wave truncation; if truncation is observed, the AV-delay will be reduced accordingly.
 - Non-invasive measurement of BP
 - Measurement of SWV
 - 10s after the last change in pacemaker settings: PCWP measurement
- Pacing-off:
 - Reprogram the pacemaker to back-up mode
 - Measurement of SWV
 - 10 seconds after pacemaker reprogramming: PCWP measurement
 - After PCWP measurement: collection of arterial and mixed venous blood samples
- Pacing-on
 - Set the pacemaker to DDD mode with a lower rate corresponding to previously determined rate with the greatest reduction in PCWP
 - 10 seconds after pacemaker reprogramming: PCWP measurement
 - After 4 respiratory cycles: collection of arterial and mixed venous blood samples
- Pacing-off

The pacing-off periods will be set at 20 bpm below the intrinsic heart rate, unlike the fixed 40 bpm backup pacing mode used at rest. During exercise, no optimal AV delay will be determined; instead, dynamic AV delay regulation will be applied and subsequently verified to ensure no truncation occurs. If truncation is detected, the AV delay will be adjusted accordingly. Additionally, blood pressure will be measured noninvasively three times

Following this protocol at 10 Watts, the procedure will be identically repeated at 25 Watts. All other procedures and considerations are identical to those described for the protocol at rest.

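### CO, SV and oxygen extraction rest on one pacing-off sample always drawn before one pacing-on sample, so change over time and carry-over cannot be separated from pacing; a closing off sample would largely fix this

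*Combined protocol and SAP*

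**What the plan says.** Sections 2.2 and 2.3 define the intrinsic-rate PCWP and SWV as the average of the pacing-off readings on either side of each pacing step. For PCWP, Appendix 3 gives the reason: "we aim to minimize the impact of spontaneous hemodynamic variability and carry-over effects".

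For CO, section 2.3 says only "The change in CO at the pacing frequency corresponding to the greatest reduction in PCWP compared to the intrinsic heart rate", and SV and oxygen extraction are worded the same way. No before-and-after reference is defined for these three. CO is VO2 divided by the arteriovenous saturation difference, and SV is CO divided by heart rate, so all three depend on the blood samples.

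Appendices 3 and 4 list arterial and mixed venous sampling twice per stage. The first is in the pacing-off block after the highest rate (+60 bpm at rest, +50 bpm in exercise); the Appendix 4 entry is "After PCWP measurement: collection of arterial and mixed venous blood samples". The second is in the final pacing-on block, which follows at once. The closing entry of the rest sequence is "Pacing-off: reprogram to pacemaker back-up mode", with no sample; the closing entry in Appendix 4 lists none either.

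Section 6.2 plans a paired t-test or a Wilcoxon test, without a period or time term, and states "A two-sided significance level of 0.05 will be used for all statistical tests". Section 2.1 says of the CO comparison that "it excludes the possibility that a reduction in PCWP is merely due to a decreased CO".

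**The concern.** With one off and one on reading in a fixed order, order and condition are the same variable. The on-minus-off difference is the pacing effect plus whatever else changed between the two draws. A CO still rising during cycling would offset a true fall or look like a gain; a falling CO would exaggerate a fall. The only off reading also comes straight after the highest pacing rate, so residue from that step enters the reference.

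The sponsor judged these influences important enough to bracket PCWP. The Fick endpoints matter because section 2.1 uses them to decide whether a lower PCWP comes at the price of forward flow. The separate SAP announced in section 6 could not repair this: a time term cannot be estimated from one off and one on sample in a fixed order.

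**Working it through.** **The plan's own figure.** Section 6.1 sizes the PCWP comparison "assuming a mean difference of -2 mmHg and a standard deviation of 2.5 mmHg". For a paired t-test (noncentral t, two-sided 5%), n=15 gives 82.1% power and n=16 gives 84.8%, so the stated 16 is adequate; 16/0.8 = 20 enrolled. This figure is for PCWP only. No effect, SD or margin is given for CO.

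**What each contrast estimates.** Let δ be the pacing effect, g the linear drift per block, C the effect of the preceding highest-rate step and r the fraction of a step's effect still present when an off sample is drawn. Apart from error:

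- off before = μ + rC
- on = μ + g + δ
- off after = μ + 2g + rδ
- planned: on − off before = δ + g − rC
- bracketed: on − mean(off before, off after) = δ − (rC + rδ)/2

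Bracketing removes g. It halves the weight of the highest-rate residue but brings in half the residue of the selected rate, so carry-over is not fully cancelled.

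**Size of drift effects.** Assumptions, none from the documents: n=20, independent reading error e = 5% of CO, between-patient SD of response b = 0, 5 or 10% of CO.

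- SD of planned difference = √(2e² + b²)
- SD of bracketed difference = √(1.5e² + b²)
- Noncentrality with no pacing effect = g√20 / SD; at g = 1% this is 0.632, 0.516 and 0.365 for the three values of b.

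| | b = 0 | b = 5% | b = 10% |
|---|---|---|---|
| SD planned | √50 = 7.07 | √75 = 8.66 | √150 = 12.25 |
| SD bracketed | √37.5 = 6.12 | √62.5 = 7.91 | √137.5 = 11.73 |
| Reduction in SE | 13% | 9% | 4% |
| False positives, planned, g = 1% | 9.2% | 7.8% | 6.4% |
| False positives, planned, g = 2% | 22.5% | 16.5% | 10.7% |
| False positives, bracketed, any linear g | 5% | 5% | 5% |
| Power for a true 5% fall, planned, no drift | 85% | 69% | 41% |
| Same, planned, g = +1% | 67% | 50% | 28% |
| Same, bracketed, no carry-over | 93% | 77% | 44% |

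With downward drift of 1% per block, the planned contrast would declare a true 5% fall significant more often (95%, 84%, 55%), because it overstates the fall.

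**How much drift is plausible in exercise.** In nominal 40 s blocks, the sampled off block is the seventh and the sampled on block the eighth, so the draws fall at about 275 s and 315 s. If CO approaches its exercise level exponentially, the change between draws is exp(−275/τ) − exp(−315/τ) of the total rise: about 0, 0.5, 1.7 and 2.9% for τ = 30, 60, 90 and 120 s (assumed). If exercise raises CO by 50% (assumed), dividing by about 3 (0.5/1.5) gives about 0, 0.2, 0.6 and 1.0% of CO per block. The 1% rows therefore match the slowest of these responses; the 2% row needs another source of drift.

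**Carry-over.** With about 35 s between the end of the highest-rate step and the off draw, r = exp(−35/τ) = 3%, 17% or 42% for washout constants of 10, 20 or 40 s (assumed).

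**The case against.** A reader might infer that the trial will miss a fall in CO, or that false-positive rates near 20% are to be expected. The documents support neither. They give no direction or size of CO drift. The two draws are in adjacent short blocks, which limits drift; the onset model above gives at most about 1% of CO per block, and at rest drift may be near zero. Larger rates also need patients to respond almost identically, which is unlikely when the tested rate is selected per patient. VO2 and heart rate are recorded continuously, so those inputs can be inspected for trend. These objections stand and limit the size of the point.

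Two objections concern the remedy. The before and after references follow different pacing rates, so with carry-over they are not exchangeable. Appendix 4 also does not say that cycling continues through the closing off block. Both must be dealt with in the text of the change.

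A reader might also infer that the primary result is affected. It is not: PCWP has its own bracketed reference.

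What the objections do not remove is the confounding. The arteriovenous difference exists at two time points only, and no later analysis can split order from pacing.

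**Conclusion.** The structural point holds: CO, SV and oxygen extraction lack the before-and-after reference given to PCWP and SWV, and pacing is fully confounded with order at every stage. The bias could go either way and its size is unknown. Under the stated assumptions (n=20, 5% reading error, linear drift of 1% of CO per block), the false-positive rate is 9.2%, 7.8% or 6.4% for between-patient SDs of 0, 5 and 10%. With no drift, bracketing still lowers the SE by 13%, 9% or 4%.

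This is mainly a concern for the 10 W and 25 W stages; at rest the gain may be precision alone. It is a cheap improvement to secondary endpoints that carry much of the interpretation. It would not by itself let a non-significant CO change rule out reduced flow, since no margin or power for CO is specified.

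**What to change.** 1. In the closing pacing-off block of Appendix 3 and of each Appendix 4 workload, add a second arterial and mixed venous sample, timed after reprogramming exactly as the first off sample. In Appendix 4, state that the workload continues until it is drawn.
2. In section 2.3, define intrinsic-rate CO, SV and oxygen extraction as the mean of the off values before and after the final pacing-on step.
3. State that the two references follow different pacing rates, so bracketing lessens the influence of the highest-rate step but does not fully cancel carry-over.
4. Clarify when the off samples are taken if the sequence ends early at the age-predicted maximum. Appendix 3 then provides only for the final pacing step, which leaves the place of the off sample unclear.

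Cost: a short amendment, three more small paired samples per participant from catheters already in place, and slightly longer cycling.

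Alternative with no added samples: by a pre-set balanced list, take the single off sample before the on step in half the participants and in the closing off block in the other half, then average the two order-specific mean differences. One mean carries +g and the other −g, so linear drift cancels. There is no precision gain, and the analysis must use the two order means so that unequal completion does not reintroduce drift.
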